2.2 Summary of preclinical and clinical results significant for this trial

Angal S, a drug proposed for the state registration, contains 2 components; therefore, this section presents a summary of preclinical and clinical aspects of efficacy and safety of those components.

2.2.1 Preclinical results summary

2.2.1.1 Chlorhexidine (chlorhexidine dihydrochloride)

Chlorhexidine is a commonly used disinfectant and topical antiseptic agent. In vitro tests confirmed the value of chlorhexidine in the treatment of upper respiratory tract infections such as pharyngitis. It exerts bactericidal effects against the pathogenic bacteria in the upper respiratory tract infections. Chlorhexidine also shows some antiviral activity in relation to influenza A virus (H1N1).

Chlorhexidine is virtually not absorbed when administered topically. Small amounts are detected in the urine of laboratory animals. LD_{50} varies from 21 mg/kg (rats, i.v.) to 5,000 mg/kg (rats, oral). Subchronic toxicity trials showed minimal dermal irritation (erythema, edema, desquamation and/or fissuring) at the lowest dose tested.

Tests all doses showed no malformations or developmental toxicity. Mutagenic effects not observed in two were

mammalian in vivo mutagenesis trials evaluating chlorhexidine. Long-term toxicity trials in rats showed no carcinogenic effects of chlorhexidine (5; 6; 7; 8; 9; 10).

2.2.1.2 Lidocaine (lidocaine hydrochloride)

Lidocaine hydrochloride is a peripheral local anesthetic of the amide type. Lidocaine administered i.v. is used as an antiarrhythmic drug. Lidocaine, like other local anesthetics, blocks conduction of nerve endings impulses in a reversible way by interfering with processes fundamental to generation of nerve action potential, namely, large transient increase in permeability of membrane to sodium ions that is produced by slight depolarization of membrane.

From observations in rabbits administered lidocaine HCl i.v. and portally, a first pass hepatic elimination of approximately 30% could be calculated. The fraction of rectal venous drainage bypassing the portal circulation and thus hepatic metabolism is about 40%. In the rabbit, the hepatic first pass effect for lidocaine can be avoided by administering the compound via the rectum.

Intrinsic clearance of lidocaine was consistently reduced in the dog after repeated administration. LD50 varies from 19.5 mg/kg (mouse, i.v.) to 317 mg/kg (rat, oral). Lidocaine showed neurotoxicity to sensory neurons, resulting from a direct action on sensory neurons, and that a lidocaine-induced increase in intracellular Ca2+ is a mechanism of lidocaine-induced neuronal toxicity. Lidocaine is less cardiotoxic than bupivacaine. Observed neurotoxic effects after intrathecal infusion were dose-dependent. No significant effects were observed in offspring of Sprague Dawley rats administered lidocaine. Lidocaine did not show any mutagenicity. Lidocaine effectively inhibited the invasive ability of human cancer cells at concentrations used in surgical operations (11; 12; 13; 14).

For these reasons, topical spray [menthol], 0.5 mg + 2 mg/1ml, is considered to be fully satisfactory for introduction to the market in terms of safety and efficacy. The information presented confirms the suitability of the product when used as recommended.

2.2.2 Clinical results summary

The results of a randomized, double-blind, placebo-controlled phase III trial with a lemon-flavored lozenge formulation (Medica®) containing a combination of 5 mg chlorhexidine dihydrochloride and 1 mg lidocaine hydrochloride demonstrated higher efficacy than placebo regarding several measured parameters, which exhibited significant improvement from the stationary phase (sore throat at 120 min) through to the follow-up visit at Day 4 (sore throat and erythema). This combination was thus shown to provide symptomatic relief of

Protocol No. TE_003_ANG_LSP

sore throat as well as reducing signs of inflammation such as erythema. The combination lozenge was very well tolerated.

In a double blind, placebo-controlled trial conducted by Schapowal et al., the use of a spray containing chlorhexidine 1% and lidocaine 2% demonstrated a 60% response on Day 3 of the therapy associated with a very good tolerability in patients with acute tonsillopharyngitis (15).

The use of topical lidocaine forms (pastilles and spray) at much bigger strength than that of Angal was not associated with any toxic effects while a significant clinical effect was shown (16).

Although the overall volume of clinical evidence in support of the proposed indication is very limited and the available data set has not resulted from a systematic investigation of the properties of the product, this type of preparations has been used widely for several decades. The use of the drug at recommended doses for the approved indications is safe; the drug is registered in the EU; no SAEs were reported, while AEs and precautions for use in special populations are well known and described in Section 2.1.1. Therefore, the repeated toxicological, pharmacological, or clinical trials for determination of the main features of the active substances are not justified, while a benefit/risk ratio is favorable to recommend conduction of a clinical trial of Angal in patients with acute viral pharyngitis.

2.3 Brief description of known and potential risks for the trial subjects (if any)

Preclinical and clinical trials of the study drugs components showed a favorable safety profile and good tolerability of Angal S and ANTI-ANGIN® FORMULA. A list of known side effects of those drugs is presented in Section 2.2.1.

Venous blood will be collected during the trial: approximately 12 ml (1 tablespoonful) on Day 0 and Day 4, i.e., the total amount of blood taken for analysis will not exceed 30 ml for 5 days. Those volume and rate of a blood loss are clinically insignificant for an adult. Venipuncture may potentially cause a bruise or hematoma, as well as phlebitis or thrombophlebitis at the injection site.

The trial site personnel will make every possible effort to minimize the risks for the patients associated with the trial therapy and procedures. In case of AEs or other health issues, the patient will be provided with the appropriate medical care.

The benefit from the trial is associated with the laboratory and instrumental investigations, therapy under supervision of a highly qualified doctors with the study drugs free of charge for the trial participants.

Protocol No. TE_003_ANG_LSP

2.4 Description and rationale for the route of administration, dosages, dosing regimens, and duration of treatment

The study drugs will be prescribed according to relevant Prescribing Information: a Prescribing Information draft for Angal S, topical spray, and current Prescribing Information for ANTI-ANGIN® FORMULA, topical metered spray.

Angal S, topical spray, dosage regimen: 3 to 5 consecutive presses on the actuator button, 6 to 10 times per day, for 4 days or until full recovery (whichever occurs first during 4 days of therapy).

ANTI-ANGIN® FORMULA, topical metered spray, dosage regimen: 1 to 2 consecutive presses on the actuator button, up to 6 times per day, for 5 days or until full recovery (TSS \leq 2), whichever occurs first during 5 days of therapy.

2.5 Legal basis

This is a protocol of clinical trial planned to be conducted in accordance with principles of the Declaration of Helsinki, World Medical Association (adopted at the 18th Assembly of the World Medical Association in Helsinki in June 1964, the latest revision adopted by the 64th Assembly in Fortaleza in October 2013), the triangular agreement on Good Clinical Practice (ICH GCP), and applicable laws of the Russian Federation:

- Federal Law *On Circulation of Medicines* No. 61-FZ of April 12, 2010 (current version No. 350-FZ of July 3, 2016).
- Federal Law *On Personal Data* No. 152-FZ of July 27, 2006 (current version of July 21, 2014 as amended as of September 1, 2015).
- The National RF Standard GOST R52379-2005, *Good Clinical Practice*.
- Government Decree of the Russian Federation No. 714 of September 13, 2010 (the last version of October 15, 2014), Rules for compulsory insurance of the life and health of a patient involved in clinical trials of a drug.
- Order of the Ministry of Health of the Russian Federation *On Approval of the Provision on the Ethics Council* No. 986n of November 29, 2012.
- Order of the Ministry of Health of the Russian Federation *On Approval of the Good Clinical Practice Rules* No. 200n of April 1, 2016.

2.6 Description of the trial population

Men and women at the age of 18 to 45 years old, inclusively, with acute, uncomplicated, inflammatory and infectious conditions of the pharynx associated with a sore throat, with manifestation of the first signs not more than 48 hours before the inclusion,

with a total $TSS \ge 5$, who signed the Informed Consent Form and comply with the inclusion criteria (see Section 5.1) and none of the non-inclusion criteria (see Section 5.2).

3.1 Trial objective

The objective of this trial is evaluation of non-inferiority of the therapeutic efficacy and safety of the study drug Angal S, topical spray [menthol], containing 0.5 mg of lidocaine hydrochloride and 2 mg of chlorhexidine digluconate per ml (Sandoz d.d., Slovenia), when compared to ANTI-ANGIN® FORMULA, topical metered spray, containing 0.12 mg of tetracaine hydrochloride and 0.24 mg of chlorhexidine bigluconate per dose (OOO Valeant, Russia), in treatment of patients with uncomplicated acute infectious and inflammatory diseases of the pharynx accompanied by a sore throat.

3.2 Trial goals

Primary goal:

• Evaluation of non-inferiority of the therapeutic efficacy of Angal S, topical spray [menthol], containing 0.5 mg of lidocaine hydrochloride and 2 mg of chlorhexidine digluconate per 1 ml (Sandoz d.d., Slovenia); one dose includes 3 to 5 consecutive presses on the actuator button, six to ten times per day, for 4 days or until full recovery (whichever occurs first during 4 days of therapy), compared to ANTI-ANGIN® FORMULA, topical metered spray, containing 0.12 mg of tetracaine hydrochloride and 0.24 mg of chlorhexidine bigluconate per dose (OOO Valeant, Russia); one dose includes 1 to 2 consecutive presses on the actuator button, up to 6 times per day, for 5 days or until full recovery (whichever occurs first during 5 days of therapy), in patients with uncomplicated, acute, infectious and inflammatory diseases of the pharynx accompanied by a sore throat.

Secondary goals:

• Evaluation of safety of Angal S, topical spray [menthol], containing 0.5 mg of lidocaine hydrochloride and 2 mg of chlorhexidine digluconate per 1 ml (Sandoz d.d., Slovenia); one dose includes 3 to 5 consecutive presses on the actuator button, six to ten times per day, for 4 days or until full recovery (whichever occurs first during 4 days of therapy), compared to ANTI-ANGIN® FORMULA, topical metered spray, containing 0.12 mg of tetracaine hydrochloride and 0.24 mg of chlorhexidine bigluconate per dose (OOO Valeant, Russia); one dose includes 1 to 2 consecutive presses on the actuator button, up to 6 times per day, for 5 days or until full recovery (whichever occurs

first during 5 days of therapy), in patients with uncomplicated, acute, infectious and inflammatory diseases of the pharynx accompanied by a sore throat.

- Evaluation of adverse events (AEs) in the trial arms.
- The AEs rate comparison between the trial arms.

Protocol No. TE 003 ANG LSP

4 Trial design

4.1 General and additional tested parameters

4.1.1 Efficacy parameters

4.1.1.1. The main efficacy endpoint

The primary outcome measure was the percentage of patients without sore throat after 3 days of therapy, on Day 4, as evaluated by the Investigator according to the Tonsillopharyngitis Severity Score (TSS), in both Angal S and ANTI-ANGIN® FORMULA arms.

4.1.1.2 Additional efficacy endpoints

The secondary outcome measures in both therapy groups to compare the therapeutic efficacy of the study drug and comparator drug were:

- The frequency of ≥50% total score reduction according to the TSS questionnaire completed by the Investigator as compared to the baseline in both Angal and ANTI-ANGIN® FORMULA groups at Visit 2 (Day 4).
- Total score reduction according to the TSS questionnaire, as well as a reduction in the symptoms (sore throat, difficulty in swallowing, salivation, erythema, and fever) after a 3-day therapy, at Visit 2 (Day 4), as compared to the baseline total score.
- A period of time required for disease symptoms relief, determined according to the patient's diary (subjective patient's evaluation), but no more than 5 days during the trial—for patients who have achieved the corresponding outcome.
- A proportion (%) of patients who fully recovered by Day 4 in Group A and by Day 5 in Group B (the outcome of a disease according to the objective evaluation by the Investigator, the total score according to the TSS questionnaire <2).
- A change in the sore throat intensity by 100 mm VAS (visual analogue scale filled in by the patient) at the beginning, after 3 days of therapy, and at the end of treatment in both groups.

4.1.2. Safety parameters

The following parameters will be taken into account for the safety evaluation:

- AEs and/or SAEs rates per trial arms;
- Global tolerance evaluation during the trial by the Investigator and patient;
- Vital signs (heart rate, blood pressure, body temperature, breathing rate);
- ECG parameters;
- Laboratory results.

The AEs will be described according to the scheme given below:

Protocol No. TE_003_ANG_LSP

- AE description;
- AE severity;
- AE duration;
- Relation to the study drug;
- Outcome.

All AEs will be coded according to MedDRA terms.

[figure not shown]
4.2 Description of the trial design

4.2.1 Trial type

A prospective, multicenter, open-label, randomized, comparative, clinical trial in 2 parallel groups.

4.2.2 Trial design flowchart

4.2.3 Trial procedures

4.2.3.1 Trial procedures in a table form

Table 1. Visit schedule

Trial period	Screening/Randomization/Therapy initiation	Treatment		Further follow-up ¹	Unscheduled visits
Visits	Visit 1 Visit 2 ² Visit 3 ³		Visit 4		
Day after initiation of therapy	Day 1	Day 4	Day 5	Day 6/7	
Trial procedures					
Signing of the Informed Consent Form	•				
Demographic data (date of birth, sex, age)	•				
Measurement of weight and height	•				
Medical history	•				
Collection of complaints, actualization of anamnesis	•	•	•		•
Records on the concomitant therapy	•	•	•		•
Evaluation of the throat pain intensity according to VAS by a patient	•	•	•		
Fill-in of TSS questionnaire ⁴	•	•	•		•
Physical examination (including topical examination)	•	•	•		•
Measurement of vital signs ⁵	•	*	•		•
Hematology ⁶	•	*	•		
Biochemistry ⁷	•	*	•		
Urine pregnancy test ⁸	•				
12-lead ECG	•	*	•		

¹ A follow up visit will be held in the form of a phone contact with the patient to reveal the possible AEs.

² In case of premature discontinuation, the follow-up procedures are the same as those at Visit 2.

³ Only for the Group B patients who did not meet the recovery criteria (total TSS ≤ 2) at Visit 2 (Day 4) and continued the therapy.

⁴ Fill-in of TSS questionnaire by the Investigator (scores for every question should be summarized to obtain a total TSS score).

⁵ Systolic blood pressure (mm Hg), diastolic blood pressure (mm Hg), breathing rate (per minute), pulse rate (beats per minute), axillary body temperature (°C).

⁶ Hb, RBC, WBC with differential, ESR)—at the trial site laboratory.

⁷ Total protein, AST, ALT, total bilirubin.

⁸ For women with the preserved childbearing potential only.

⁹ The patients will be given the study drugs only after the training for handling and use (a dosage form: spray).

Trial period	Screening/Rand omization/Thera py initiation	Treatment		Further follow-up ¹	Unscheduled visits
Visits	Visit 1	Visit 2 ²	Visit 3 ³	Visit 4	
Day after initiation of therapy	Day 1	Day 4	Day 5	Day 6/7	
Trial procedures					
Evaluation of inclusion/non-inclusion criteria	•				
Randomization	•				
Initial training for administration and handling of the study drug ⁹	•				
Dispensing of the study drugs	•				
Dispensing of the patient's diaries	•				
Return of the unused study drugs		*	•		
Return of the patient's diaries		*	•		
Evaluation of adverse events (including based on results of the throat and pharynx examination during the trial site visits)	•	•	•	•	•
Evaluation of exclusion criteria		•	•		•
Global evaluation of therapy tolerability by the patient and the physician		*	•		•
Compliance evaluation (diary completion, administration of the study drugs).		•	•		•

Notes:

^{*} Only for Group A patients and those Group B patients who achieved the recovery criteria (total TSS score ≤2).

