4.2.4.2 Efficacy evaluation visit (Visit 2, Day 4)

Visit 2 is conducted on Day 4; the patient must visit the trial site in the fasted state and bring the filled-in diary and unused drug.

If Group B patients (ANTI-ANGIN® FORMULA) did not meet recovery criteria (total $TSS \le 2$) at Visit 2 (Day 4), they will require continuation of the therapy, and some procedures for those patients will be transferred for the next day (Visit 3, Day 5), see below. The patients will keep their diaries and the unused drugs.

Visit 2 procedures for both groups:

- Collection of complaints, actualization of anamnesis;
- Records on the concomitant therapy;
- Physical examination (including oropharynx);
- Measurement of the main vital signs;
- Evaluation of adverse events (including based on results of the throat and pharynx examination);
- Evaluation of exclusion criteria;
- Compliance evaluation (diary completion, administration of the study drugs);

Visit 2 procedures for patients from Group A (Angal S) and Group B (ANTI-ANGIN® FORMULA) who achieved recovery criteria (total TSS \leq 2):

- Hematology;
- Biochemistry;
- 12-lead ECG;

- Global evaluation of treatment tolerability during the trial by the physician and the patient;
- Return of the unused study drug;
- Return of the patient's diary;

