4.2.4.3 Trial completion visit for Group B patients (Visit 3, Day 5)

This visit is for Group B patients only (ANTI-ANGIN® FORMULA) who did not achieve the recovery criteria (total TSS score ≤ 2) at Visit 2 (Day 4).

Visit 3 is conducted on Day 5; the patient must visit the trial site in the fasted state and bring the filled-in diary and unused drug.

Visit 3 procedures:

- Collection of complaints, actualization of anamnesis;
- Records on the concomitant therapy;
- Physical examination (including oropharynx);
- Measurement of the main vital signs;
- Evaluation of adverse events (including based on results of the throat and pharynx examination);
- Evaluation of exclusion criteria;
- Return of the unused study drug;
- Return of the patient's diary;
- Compliance evaluation (diary completion, administration of the study drugs);
- Hematology:
- Biochemistry;
- 12-lead ECG;
- Global evaluation of treatment tolerability during the trial by the physician and the patient.

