9.1.4 Safety parameters analysis

A descriptive part of the safety analysis will include an evaluation of incidences and two-sided CI 95% for the following parameters in every trial group:

- AEs: the incidence in total and for separate categories (according to MedDRA), for the trial and by groups;
- SAEs: the incidence in total and for separate categories (according to MedDRA), for the trial and by groups;
- Incidence of clinically significant changes of the physical examination results by visits and groups;
- Incidence of clinically significant changes of the laboratory results by visits and groups;
- Incidence of clinically significant changes of the vital signs (body temperature, BP, pulse rate, HR) by visits and groups;
- Incidence of clinically significant changes of the ECG parameters by visits and groups;
- Global tolerance evaluation during the trial by the Investigator and patient.

The Fisher's exact test will be used to compare incidences between the groups, and chi-square will be used to compare the global therapy tolerability by the Investigator and patient. The McNemar's test will be used to evaluate for the dynamic changes during the trial (before—after) for all the repeatedly evaluated incidences in every group.

In addition to the incidence, all the quantitative safety parameters will be presented in a table form (laboratory results, vital signs, ECG) by visits and groups. The difference will be evaluated using 2-way-ANOVA (group and visit numbers will serve as the relevant factors). The post-hoc criteria will be used in case of significant difference.

Safety analysis will be performed on the safety population.

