4.1.5 Analysis of laboratory and functional tests results

A between group comparison of the vital signs changes (systolic blood pressure, diastolic blood pressure, breathing rate, heart rate, body temperature) revealed at every visit (Visits 1, 2, 3) as well as laboratory results and ECG changes incidence obtained at Visit 1 and Visits 2–3 is envisaged. In addition, significance of the changes will be evaluated for all repeatedly measured parameters.

The following laboratory parameters will be reviewed:

- Hematology
 - o Hemoglobin
 - o RBC
 - o ESR
 - o WBC
 - o Neutrophils
 - Juvenile
 - Stab
 - Segmented
 - o Eosinophils
 - o Basophils
 - o Monocytes
 - o Lymphocytes
- Biochemistry
 - Total protein
 - o AST
 - o ALT
 - o Total bilirubin

ANOVA methods will be used to reveal a simultaneous influence of a group and time factors on the quantitative parameters.

The cross tables analysis will be used to reveal a correlation between the qualitative parameters (chi-squared test).

For the quantitative parameters, a comparison will be made by Student's t-test for the independent samples (in case of confirmation of hypothesis on normal variables distribution) or Mann–Whitney test (in case of rejection of hypothesis on normal

variables distribution); for the qualitative parameters—using Fisher's exact test.

To evaluate significance of the intragroup changes during the trial for repeatedly measured parameters, the paired Student's t-test (in case of confirmation of hypothesis on normal variables distribution) or paired Wilcoxon signed-rank test (in case of rejection of hypothesis on normal variables distribution) will be used; for the qualitative parameters McNemar's test will be used.

5 Presentation of statistical analysis results

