Arm	Parameter	Total protein	ALT	AST	Total bilirubin
	n				
	M				
	SD				
	95% CI				
	Min.				
	Max.				
	Me				
	IQR				
	n				

M		
SD		
95% CI		
Min.		
Max.		
Me		
IQR		
р		

Table 12.A number of patients with normal and abnormal hematology parameters (Visits 1, 2, 3)

Arm	Parameter	Hemoglobin	RBC	ESR	WBC
	Reference				
	Deviation				
	Reference				
	Deviation				

Table 13.A number of patient with normal and abnormal WBC differential results (Visits 1, 2, 3)

Arm	Parameter	Neutrophils, total	Juvenile	Stab	Segmented	Eosinophils	Basophils	Monocytes	Lymphocytes
	Reference								
	Deviation								
	Reference								
	Deviation								

Table 14. A number of patient with normal and abnormal biochemistry parameters (Visits 1, 2, 3)

Arm	Parameter	Total protein	ALT	AST	Total bilirubin
	Reference				
	Deviation				
	Reference				
	Deviation				

Table 15. Concomitant diseases

Organ, system	Arm	Number of diseases (proportion, %)
		n/N (%)

Table 16. Concomitant therapy

Drug group	Arm	Number of prescriptions (proportion, %)
		n/N (%)

	n/N (%)
	n/N (%)
	n/N (%)
	n/N (%)

Table 17. Evaluation of throat pain severity according to VAS

Arm	Parameter	Visit 1	Visit 2	Visit 3
	n			
	M			
	SD			
	95% CI			
	Min.			
	Max.			
	Me			
	IQR			
	n			
	M			
	SD			
	95% CI			
	Min.			
	Max.			
	Me			
	IQR			
	p			

Table 18. TSS scores (Visits 1, 2, 3)

Arm	Amount of scores	Sore throat	Difficulty in swallowing	Salivation	Pharyngeal mucosa hyperemia	Fever
	0	n/N (%)	n/N (%)	n/N (%)	n/N (%)	n/N (%)
	1	n/N (%)	n/N (%)	n/N (%)	n/N (%)	n/N (%)
	2	n/N (%)	n/N (%)	n/N (%)	n/N (%)	n/N (%)
	3	n/N (%)	n/N (%)	n/N (%)	n/N (%)	n/N (%)
	0	n/N (%)	n/N (%)	n/N (%)	n/N (%)	n/N (%)
	1	n/N (%)	n/N (%)	n/N (%)	n/N (%)	n/N (%)
	2	n/N (%)	n/N (%)	n/N (%)	n/N (%)	n/N (%)
	3	n/N (%)	n/N (%)	n/N (%)	n/N (%)	n/N (%)
	p	n/N (%)	n/N (%)	n/N (%)	n/N (%)	n/N (%)

Table 19. Frequency of the recovery criteria achievement (total $TSS \le 2$) by Visits 2, 3

Arm	Parameter	Visit 2	Visit 3
	Criterion is met		
	Criterion is not met		
	Criterion is met		
	Criterion is not met		

Table 20. Global evaluation of treatment tolerability (Visits 2, 3)

Arm	Parameter	Tolerability evaluation by the patient	Tolerability evaluation by the physician
	n		
	M		

SD	
95% CI	
Min.	
Max.	
Me	
IQR	
n	
M	
SD	
95% CI	
Min.	
Max.	
Me	
IQR	
р	

Table 21. Registered adverse events occurred after initiation of the trial therapy

	Mile	d AEs	Moder	ate AEs	Seven	re AEs	To	otal	Total

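### By-visit lab, ECG and tolerability comparisons set all of Group A against only the recovered part of Group B at Visit 2, and have no Group A data at Visit 3

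*Protocol*

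**What the plan says.** **Who is measured when.** Protocol 4.2.3.1, Table 1, stars haematology, biochemistry, 12-lead ECG and global tolerability at Visit 2 (Day 4). The note to the star reads "Only for Group A patients and those Group B patients who achieved the recovery criteria", defined as total TSS ≤2. Section 4.2.4.2 agrees: for comparator patients not yet recovered, "some procedures for those patients will be transferred for the next day (Visit 3, Day 5"). Visit 3 is footnoted "Only for the Group B patients who did not meet the recovery criteria", and section 4.2.4.3 says "This visit is for Group B patients only (ANTI-ANGIN® FORMULA) who did not achieve the recovery criteria". No Group A patient has a scheduled Visit 3.

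**What is analysed.** Protocol 9.1.4 lists "Incidence of clinically significant changes of the laboratory results by visits and groups", has a matching item for ECG, and compares incidences between groups with Fisher's exact test. Quantitative labs, vital signs and ECG are also tabulated by visit and group, and tested in a two-way ANOVA with group and visit number as factors. SAP 4.1.5 keeps an ANOVA on group and time. In SAP 5.1, Tables 9–11 (labs) are headed Visits 1, 2, 3 and have a p row. So does "Table 20. Global evaluation of treatment tolerability (Visits 2, 3"). Tables 8 and 12–14 are by visit without a p row.

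**What points the other way.** SAP 4.1.5 compares vital signs "revealed at every visit (Visits 1, 2, 3"), but labs and ECG at Visit 1 and at Visits 2–3. Protocol 4.2.3.2.5 and 4.2.3.2.6 have tolerability rated, and post-baseline blood drawn, at Visit 2 or Visit 3 as applicable. Neither document defines a combined time point.

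**Vital signs.** Table 1 also stars these at Visit 2, while 4.2.4.2 puts "Measurement of the main vital signs" among the procedures for both groups, as does SAP 3.8.2.

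**The concern.** Randomisation protects a comparison only while both arms contribute all their patients, or lose them for reasons unrelated to outcome. Here a Group B patient supplies a Visit 2 lab, ECG or tolerability value only after recovering, whereas Group A patients supply one either way. Unrecovered Group B patients appear only at Visit 3, where there is nobody to compare them with.

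For any measure that tracks recovery, the comparator would tend to look better at Visit 2 even if the two sprays were identical. Plausible candidates are ESR, WBC and a tolerability rating given in an open-label trial. Protocol 3.1 names safety alongside efficacy in the trial objective, so a misleading p-value in these tables could be read as a safety or tolerability signal against the study drug. No missing-data rule repairs this: under Protocol 9.5 and SAP 3.6, everything other than the primary endpoint is analysed as available.

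**Working it through.** The plan states no figure for these comparisons, so there is none to reproduce. The check has two parts.

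**1. Patients per cell.** Inputs: 128 completers per arm (Protocol 9.2) and r, the Group B proportion with TSS ≤2 on Day 4. The documents do not give r. The nearest figure is the 63% comparator rate for absence of sore throat in Protocol 9.2, which is a different endpoint, so r is varied. Group B supplies 128 × r patients at Visit 2 and 128 × (1 − r) at Visit 3.

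| r (assumed) | Visit 2: A vs B | Visit 3: A vs B |
|---|---|---|
| 0.40 | 128 vs 51 | 0 vs 77 |
| 0.50 | 128 vs 64 | 0 vs 64 |
| 0.63 | 128 vs 81 | 0 vs 47 |
| 0.75 | 128 vs 96 | 0 vs 32 |
| 0.85 | 128 vs 109 | 0 vs 19 |

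The Group A / Visit 3 cell is empty for every r. In the ANOVA, a group-by-visit interaction is then not estimable at Visit 3. Without an interaction, the Visit 3 term simply fits the Group B mean there, so the only post-baseline values of unrecovered Group B patients add nothing to the group contrast.

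**2. Bias at Visit 2 with identical drugs.** Let D be the gap, in SD, between unrecovered and recovered patients (assumed). Taking recovered patients as zero, Group A has mean (1 − r) × D and the Group B patients measured have mean 0. The bias is therefore (1 − r) × D.

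By hand, with r = 0.65, D = 0.5 and the 140 per arm randomised:
- Group B at Visit 2: 140 × 0.65 = 91
- Bias: 0.35 × 0.5 = 0.175 SD
- Standard error: √(1/140 + 1/91) = 0.135 SD
- Ratio: 0.175 / 0.135 = 1.30, so a two-sided 5% test rejects about 25% of the time

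By simulation (128 per arm, two-sample t-test, 4,000 runs, no true difference), each cell shows bias in SD and then the rejection rate:

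| r | D = 0.3 | D = 0.5 | D = 1.0 |
|---|---|---|---|
| 0.50 | 0.15; 16% | 0.25; 35% | 0.50; 85% |
| 0.63 | 0.11; 12% | 0.19; 24% | 0.37; 68% |
| 0.75 | 0.08; 9% | 0.13; 14% | 0.25; 42% |

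In the same runs, using one end-of-treatment value per patient (128 vs 128) gave rejection rates of 4.6% to 5.6% throughout. That assumes no change between Day 4 and Day 5.

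**The case against.** The best defence is that the plan already implies the remedy. Each patient has one scheduled post-baseline lab sample, ECG and tolerability rating. In a single sentence SAP 4.1.5 separates vital signs (each visit) from labs and ECG (Visits 2–3), which reads naturally as one pooled time point. This stands as evidence of a possible intention. It does not settle the matter: the pooling is nowhere defined, and the table shells with p rows and the visit-number ANOVA say otherwise. A programmer following them would produce the selected comparison.

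It is also fair that the consequence is limited. SAP section 4 confines the non-inferiority conclusion to the primary parameter and treats safety variables as of research interest. TSS and adverse events are collected at Visit 2 in both groups.

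A reader might infer more than the documents support, in four ways:

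- *That Protocol 9.1.4 itself analyses tolerability by visit.* It does not. That item covers the trial as a whole, with one chi-square test; only SAP Table 20 splits it by visit.
- *That every safety parameter is biased.* Bias requires that the parameter track recovery. It may be near zero for total protein, and nothing in the documents shows a gradient for the others. The eligibility criteria on leukocytosis and ESR may narrow it even for WBC and ESR.
- *That body temperature is a clear example.* Temperature is a TSS component, and TSS is unstarred at Visit 2, so everyone needs a reading. Entry also requires a temperature below 37.5 °C.
- *That 25% is this trial's error rate.* It is one point in an assumed grid.

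**Conclusion.** The structural fault is certain from the documents. As written, the between-arm lab and ECG analyses by visit in Protocol 9.1.4, and the p-values in SAP Tables 9–11 and 20, compare all of Group A with a recovery-selected part of Group B at Visit 2 and have no Group A data at Visit 3.

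The size is not certain. It rests on r and D, both assumed. Over r of 0.50 to 0.75 and D of 0.3 to 1.0 SD, the bias runs from 0.08 to 0.50 SD and false rejection from 9% to 85%, and it falls to nothing for a parameter unrelated to recovery.

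The primary endpoint and adverse-event counts are untouched, so the main conclusion is not at risk. The point should still be settled before analysis, because the safety tables would otherwise carry p-values that cannot be interpreted.

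**What to change.** 1. In SAP 4.1.5, define Visits 2–3 as one end-of-treatment record per patient: Visit 2 for Group A and recovered Group B, Visit 3 for continuing Group B.
2. Make all between-arm lab, ECG and tolerability tests on that record.
3. In the ANOVA, replace visit number with baseline versus end of treatment. This departs from Protocol 9.1.4, so document it under Protocol 9.6. The statement in SAP section 1 that no changes from the protocol are envisaged then needs amending.
4. Keep the by-visit tables as descriptive listings and remove the p rows from Tables 9–11 and 20 in that form.
5. Report Visit 3 vital signs (Table 7) and VAS (Table 17) descriptively, for Group B only.
6. Reconcile the star on Visit 2 vital signs in Table 1 with Protocol 4.2.4.2 and SAP 3.8.2, which list them for both groups.

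**Cost.** One derivation rule, revised table shells and a documented change to the ANOVA, with no new visits, samples or patients. The remaining weakness is that the end-of-treatment record falls one day later for continuing Group B patients; the report should say so.
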